8.3.5 Postvaccination Observation Period (30 Minutes)

All participants will be observed for at least 30 minutes after each vaccination for any immediate reactions. If any immediate AEs (including allergic reactions) are observed during this period, the time at which the event occurred within this timeframe, as well as the event itself, any concomitant medications that were administered, and resolution of the event, must be recorded on the appropriate eCRF.

8.3.6 Pregnancy Testing

- Pregnancy testing
 - Pregnancy testing requirements for study exclusion are described in Section 5.2.
 - Pregnancy testing (urine) should be conducted prior to vaccination at Visit 1 and Visit 3.
 - For participants who become pregnant after receiving a study vaccination, study visits and vaccination will be paused until resolution of the pregnancy (e.g. term, elective termination, spontaneous abortion). Study visits and study vaccination in pregnancy participants will be handled as described in Table 3. Breastfeeding is not a contraindication to receiving study vaccinations. Pregnancy and exposure during breastfeeding must be reported as described in Section 8.4.5.
 - Additional serum or urine pregnancy tests may be performed, as determined necessary by the investigator to establish the absence of pregnancy at any time during the participant's participation in the study.

Table 3 Guidelines for Pregnant Participants: Managing Study Visits and Study Vaccinations

Visit Where Pregnancy is Detected	Action				
Day 1	Do not enroll the participant				
	No scheduled visits until resolution of the pregnancy (e.g. term, elective termination, spontaneous abortion).				
Between First and Second Vaccination Visits	• The second study vaccination visit should be administered at least 4 weeks following resolution of pregnancy, after normalization of β-human chorionic gonadotropin (β-hCG), and in accordance to the intervention group assigned and visit windows in Section 1.3.				
	Continue with scheduled study visits during the pregnancy.				
After Second Vaccination Visits	• Safety follow-up will be conducted after resolution of the pregnancy (e.g. term, elective termination, spontaneous abortion).				

8.4 Adverse Events, Serious Adverse Events, and Other Reportable Safety Events

The definitions of an AE or SAE, as well as the method of recording, evaluating, and assessing causality of AE and SAE and the procedures for completing and transmitting AE, SAE, and other reportable safety event reports can be found in Appendix 3.

Adverse events, SAEs, and other reportable safety events will be reported by the participant (or, when appropriate, by a caregiver, surrogate, or the participant's legally authorized representative).

The investigator and any designees are responsible for detecting, documenting, and reporting events that meet the definition of an AE or SAE as well as other reportable safety events. Investigators remain responsible for following up AEs, SAEs, and other reportable safety events for outcome according to Section 8.4.3.

The investigator, who is a qualified physician, will assess events that meet the definition of an AE or SAE as well as other reportable safety events with respect to seriousness, intensity and causality.

8.4.1 Time Period and Frequency for Collecting AE, SAE, and Other Reportable Safety Event Information

All AEs, SAEs, and other reportable safety events that occur after the participant's legally acceptable representative provides documented informed consent but before allocation/randomization must be reported by the investigator if they cause the participant to be excluded from the study, or are the result of a protocol-specified intervention, including but not limited to washout or discontinuation of usual therapy, diet, placebo, or a procedure.

From the time of allocation/randomization through 14 days following the first vaccination(s) and from the time of any subsequent vaccination(s) through 14 days thereafter, all AEs, SAEs, and other reportable safety events must be reported by the investigator. All SAEs and other reportable safety events that occur from the time of allocation/randomization through 6 months following the last vaccination must be reported by the investigator, regardless of whether the events are considered to be vaccine-related by the investigator.

Additionally, any SAE brought to the attention of an investigator at any time outside of the time period specified in the previous paragraph also must be reported immediately to the Sponsor if the event is either:

- A death that occurs prior to the participant completing the study, but outside the time period specified in the previous paragraph.

OR

 An SAE that is considered by an investigator, who is a qualified physician, to be vaccine related.

Investigators are not obligated to actively seek AEs or SAEs or other reportable safety events in former study participants. However, if the investigator learns of any SAE, including a death, at any time after a participant has been discharged from the study, and he/she considers the event to be reasonably related to the study intervention or study participation, the investigator must promptly notify the Sponsor.

All initial and follow-up AEs, SAEs, and other reportable safety events will be recorded and reported to the Sponsor or designee within the time frames as indicated in Table 4.

Table 4 Reporting Time Periods and Time Frames for Adverse Events and Other Reportable Safety Events

Type of Event	Reporting Time Period: Consent to Randomization/ Allocation	Reporting Time Period: Randomization/ Allocation through Protocol-specified Follow-up Period	Reporting Time Period: After the Protocol- specified Follow-up Period	Time Frame to Report Event and Follow-up Information to Sponsor:
NSAE	Report if: - due to protocol- specified intervention - causes exclusion - participant is receiving placebo run- in or other run-in treatment	Report all	Not required	Per data entry guidelines
SAE	Report if: - due to protocol- specified intervention - causes exclusion - participant is receiving placebo run- in or other run-in treatment	Report all	Report if: - drug/vaccine related any death until participant completion of study (Follow ongoing to outcome)	Within 24 hours of learning of event
Pregnancy/ Lactation Exposure	Report if: - participant has been exposed to any protocol-specified intervention (eg, procedure, washout or run-in treatment including placebo run-in)	Report all	Previously reported - Follow to completion/ termination; report outcome	Within 24 hours of learning of event
Cancer	Report if: - due to intervention - causes exclusion	Report all	Not required	Within 5 calendar days of learning of event (unless serious)
Overdose	Report if: - receiving placebo run- in or other run-in medication	Report all	Not required	Within 5 calendar days of learning of event

NSAE=nonserious adverse event; SAE=serious adverse event

8.4.2 Method of Detecting AEs, SAEs, and Other Reportable Safety Events

Care will be taken not to introduce bias when detecting AEs and/or SAEs and other reportable safety events. Open-ended and nonleading verbal questioning of the participant is the preferred method to inquire about AE occurrence.

8.4.3 Follow-up of AE, SAE, and Other Reportable Safety Event Information

After the initial AE/SAE report, the investigator is required to proactively follow each participant at subsequent visits/contacts. All AEs, SAEs, and other reportable safety events, including pregnancy and exposure during breastfeeding, cancer, and overdose will be followed until resolution, stabilization, until the event is otherwise explained, or the participant is lost to follow-up (as defined in Section 7.3). In addition, the investigator will make every attempt to follow all nonserious AEs that occur in allocated/randomized participants for outcome. Further information on follow-up procedures is given in Appendix 3.

8.4.4 Regulatory Reporting Requirements for SAE

Prompt notification (within 24 hours) by the investigator to the Sponsor of SAE is essential so that legal obligations and ethical responsibilities towards the safety of participants and the safety of a study intervention under clinical investigation are met.

The Sponsor has a legal responsibility to notify both the local regulatory authority and other regulatory agencies about the safety of a study intervention under clinical investigation. The Sponsor will comply with country-specific regulatory requirements and global laws and regulations relating to safety reporting to regulatory authorities, IRB/IECs, and investigators.

Investigator safety reports must be prepared for SUSARs according to local regulatory requirements and Sponsor policy and forwarded to investigators as necessary.

An investigator who receives an investigator safety report describing an SAE or other specific safety information (eg, summary or listing of SAE) from the Sponsor will file it along with the IB and will notify the IRB/IEC, if appropriate according to local requirements.

8.4.5 Pregnancy and Exposure During Breastfeeding

Although pregnancy and infant exposure during breastfeeding are not considered AEs, any pregnancy or infant exposure during breastfeeding in a participant (spontaneously reported to the investigator or their designee) that occurs during the study are reportable to the Sponsor.

All reported pregnancies must be followed to the completion/termination of the pregnancy.

Any pregnancy complication will be reported as an AE or SAE.

The medical reason (example: maternal health or fetal disease) for an elective termination of a pregnancy will be reported as an AE or SAE. Prenatal testing showing fetus will be born with severe abnormalities/congenital anomalies that leads to an elective termination of a pregnancy will be reported as an SAE for the fetus.

Pregnancy outcomes of ectopic pregnancy, spontaneous abortion, missed abortion, benign hydatidiform mole, blighted ovum, fetal death, intrauterine death, miscarriage, and stillbirth must be reported as serious events (Important Medical Events). If the pregnancy continues to term, the outcome (health of infant) must also be reported.

PROTOCOL/AMENDMENT NO.: 066-02

8.4.6 Disease-related Events and/or Disease-related Outcomes Not Qualifying as AEs or SAEs

56

None.

8.4.7 Events of Clinical Interest

None.

8.5 Treatment of Overdose

In this study, an overdose is defined as a participant receiving >1 dose of study vaccine in a 24-hour period, or >3 doses of study vaccine throughout the study.

Sponsor does not recommend specific treatment for an overdose.

Decisions regarding dose interruptions or modifications will be made by the investigator in consultation with the Sponsor Clinical Director based on the clinical evaluation of the participant.

8.6 Pharmacokinetics

PK parameters will not be evaluated in this study.

8.7 Pharmacodynamics

Pharmacodynamic parameters will not be evaluated in this study.

8.8 Future Biomedical Research Sample Collection

If the participant's legally acceptable representative provides documented informed consent for FBR, the following specimens will be obtained as part of FBR:

DNA for future research

8.9 Visit Requirements

Visit requirements are outlined in Section 1.3. Specific procedure-related details are provided in Section 8.

8.9.1 Screening

The screening visit or the last screening visit (for re-screening) should be on the same day of randomization and the first dose of vaccination. Potential participants will be evaluated to determine that they fulfill the entry requirements as set forth in Section 5. Screening procedures may be repeated after consultation with the Sponsor.

57

If possible, all Day 1 visit procedures should be performed on the day of consent. If date of Day 1 visit (and all procedures) is later than consent date, the interval between the date of consent and the date of the Day 1 visit should be no more than 14 days. If the interval is 15 days or longer, then the participant's legally acceptable representative must be reconsented.

8.9.2 Prerequisites for Vaccination Visits (Day 1, Month 2, and Month 6)

This section summarizes prerequisites for vaccination visits. See the inclusion/exclusion criteria for specific restrictions on Day 1 (see Section 5.1 and Section 5.2). At Month 2 (only for 3-dose boy arm) and Month 6 study vaccination visits, study personnel should verify by questioning the participant's legally acceptable representative and/or by examination that:

- 1. The participant has not had a fever (oral temperature ≥37.5°C) within the 24-hour period prior to the vaccination visit.
- 2. The participant has not received any systemic (oral or parenteral) corticosteroids in 14 days prior to any study vaccination visits.
- 3. The participant has not received a non-study inactivated or recombinant vaccine within 14 days prior to any study vaccination visit or a non-study live vaccine within 28 days prior to any study vaccination visit.

If the participant does not meet the requirements listed above, the study visit (including specimen collection and study vaccination) should be re-scheduled.

8.9.3 Discontinued Participants Continuing to be Monitored in the Study

Participants who discontinue study vaccinations but continue in the study will attend study visits per the SoA (Section 1.3). However, serum will not be collected at the Month 7 study visit or subsequent visits from participants who did not complete the specified study vaccination regimen.

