8.1.10 Discontinuation and Withdrawal

Participants who discontinue study intervention prior to completion of the scheduled vaccination regimen should be encouraged to continue to be followed for all remaining study visits as outlined in the SoA and Section 8.9.3.

Participants who withdraw from the study should be encouraged to complete all applicable activities scheduled for the next study visit (exception: serum sample collection should not be performed unless the participant has received all scheduled doses of the study vaccine) at the time of withdrawal. Any AEs that are present at the time of withdrawal should be followed in accordance with the safety requirements outlined in Section 8.4.

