9 STATISTICAL ANALYSIS PLAN

This section outlines the statistical analysis strategy and procedures for the study. Changes to analyses made after the protocol has been finalized, but prior to final database lock, will be documented in a supplemental statistical analysis plan (sSAP) and referenced in the Clinical Study Report (CSR) for the study. Post hoc exploratory analyses will be clearly identified in the CSR.

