9.5 Analysis Populations

9.5.1 Immunogenicity Analysis Populations

Per-Protocol Immunogenicity (PPI) Population

The PPI population will serve as the primary population for the analysis of immune response to each HPV-types. To be included in this population, participants must:

- (1) Have received all required vaccinations of 9vHPV vaccine with the correct dose within acceptable day ranges (see Table 5).
- (2) Have provided blood samples for serology testing within 21 to 49 days post last dose.
- (3) Be seronegative to the appropriate HPV type(s) at Day 1.

(4) Have no other protocol violations that could interfere with the evaluation of participant's immune response to the study vaccine.

61

The final determination on protocol violations, which will be used for determining the PPI population, will be made prior to the database lock and will be documented in a separate memo.

Table 5 Acceptable Day Ranges for Vaccination Visits

	Protocol Specified	Day Range for Inclusion in Statistical Analysis				
Vaccination Dose	Visit Window	(Relative to Day 1 [†])				
	3-Dose [0,2,6 re	gimen]				
Dose 1	Day 1 [†]	0				
Dose 2	Month 2 ± 3 weeks	36 to 84				
Dose 3	Month 6 ± 4 weeks	148 to 218				
	2-Dose [0,6 regimen]					
Dose 1	Day 1 [†]	0				
Dose 2	Month 6 ± 4 weeks	148 to 218				
† Day 1 refers to the date wh	en vaccination dose 1 was administer	ed.				

Table 6 Acceptable Day Ranges for Collection of Serum Samples

Study Visit	Sample Type	Target Collection Day (Relative to Day 1)†	Day Range for Inclusion in Statistical Analysis (Relative to Day 1†)			
Day 1	Serum	0	-14 to 0			
Month 7	Serum	30 days post last dose	21 to 49 post last dose			
Month 18	Serum	548	366 to 730			
Month 30	Serum	913	731 to 1004			
† Day 1 refers to the date when vaccination dose 1 was administered. For Month 7, indicated target collection/day range						
is relative to date	is relative to date of injection of last dose of 9vHPV vaccine.					

All Naïve Participants with Serology (ANPS) Population

A supportive immunogenicity analysis will be carried out on the all type-specific naïve participants with serology population. To be included in this population, participants must:

- (1) Have received at least 1 vaccination.
- (2) Have provided serum samples with evaluable results.
- (3) Be seronegative to the appropriate HPV types at Day 1.

For each of the PPI and ANPS analysis populations:

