9.6 Statistical Methods

9.6.1 Statistical Methods for Immunogenicity Analyses

Estimation of percent seroconversion

Within a study arm, the point estimate of percent seroconversion is calculated as the percent of participants with evaluable serology result at 1 month post last dose (Month 7) who seroconvert at 1 month post last dose (Month 7), where seroconversion is as defined in Section 9.4.1. Calculation of the corresponding 95% CI is based on the exact binomial method proposed by Clopper and Pearson (1934).

Estimation of percent seropositivity

For each of the Months 18 and 30 time points, within a study arm, the point estimate of percent seropositivity for a given HPV type is calculated as the percent of participants with evaluable serology result with cLIA titer at or above the serostatus cutoff for the given HPV type. Calculation of the corresponding 95% CI is based on the exact binomial method proposed by Clopper and Pearson (1934).

Estimation of GMTs

Within a study arm, GMTs and corresponding 95% CI will be derived by taking the antilogarithm of the mean and corresponding 95% CI (calculated based on the t-distribution) of the mean of the log-transformed anti-HPV titers. Anti-HPV titers reported as less than the LLOQ of the relevant anti-HPV type will be replaced by the half of the LLOQ in the log-transformation of anti-HPV titers.

PRODUCT: V503
PROTOCOL/AMENDMENT NO.: 066-02

Table 7 Analysis Strategy for Immunogenicity Variables

Endpoint/Variable (Description, Time Point)	Primary vs. Supportive Approach	Statistical Method	Analysis Population	Missing Data Approach	
Primary Endpoints				_	
Seroconversion to each HPV 6, 11, 16, 18, 31, 33, 45, 52 and 58 at 1	Р	Point estimate, 95% CI by exact	PPI	Observed	
month post last dose (Month 7) following 3 doses of 9vHPV vaccine	S	binomial method	ANPS	data only	
Seroconversion to each HPV 6, 11, 16, 18, 31, 33, 45, 52 and 58 at 1	P	Point estimate, 95% CI by exact	PPI	Observed	
month post last dose (Month 7) following 2 doses of 9vHPV vaccine	S	binomial method	ANPS	data only	
Secondary Endpoints	!	-1			
GMTs to each HPV 6, 11, 16, 18, 31, 33, 45, 52 and 58 at 1 month post last	P	Point estimate	PPI	Observed	
dose (Month 7) following 3 doses of 9vHPV vaccine	S	and 95% CI	ANPS	data only	
GMTs to each HPV 6, 11, 16, 18, 31, 33, 45, 52 and 58 at 1 month post last	Р	Point estimate	PPI	Observed	
dose (Month 7) following 2 doses of 9vHPV vaccine	S	and 95% CI	ANPS	data only	

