9.11 Compliance (Medication Adherence)

Compliance is defined in this study as receipt of all scheduled study vaccinations. To summarize compliance, the numbers of participants who receive each vaccination will be tabulated. Compliance with the planned vaccination schedule (3-dose: Day 1, Month 2, Month 6, 2-dose: Day 1, Month 6) will be described by histograms of actual intervals between vaccinations relative to the expected interval.

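### Does the supportive ANPS population need redefining because children who miss a dose give no post-vaccination serum?

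*Combined protocol and SAP*

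**What the plan says.** Section 9.5.1 sets three conditions for ANPS: "Have received at least 1 vaccination", "Have provided serum samples with evaluable results", and type-specific seronegativity at Day 1. The second condition names no visit. PPI shares the serostatus condition ("Be seronegative to the appropriate HPV type(s) at Day 1") but also requires the full regimen at the correct dose within the Table 5 day ranges, Month 7 serum 21 to 49 days after the last dose, and no other interfering protocol violation.

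Two sections on conduct limit who can give serum. Under 8.9.3, for children who stop vaccination but stay in the study, "serum will not be collected at the Month 7 study visit or subsequent visits from participants who did not complete the specified study vaccination regimen". Under 8.1.10, for children who withdraw, "serum sample collection should not be performed unless the participant has received all scheduled doses of the study vaccine". Section 8.2.1 schedules serum before the first dose on Day 1 and then at Months 7, 18 and 30, so no sample is planned between doses.

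On the analysis side, 9.6.1 defines percent seroconversion as the "percent of participants with evaluable serology result at 1 month post last dose (Month 7) who seroconvert". Table 7 describes each Month 7 row, PPI and ANPS alike, as following 3 doses or following 2 doses, with observed data only. For compliance, 9.11 states that "the numbers of participants who receive each vaccination will be tabulated", and 9.6.3 summarises vaccinated participants and reasons for discontinuation by arm.

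**The concern.** A supportive population with a one-dose entry rule looks like a check on whether the per-protocol result survives when partly vaccinated children are included. The sampling rules in 8.9.3 and 8.1.10 make that check impossible, and 9.5.1 does not refer to them. A reader who sees PPI and ANPS agree could conclude that non-completion does not matter, when the data cannot speak to it.

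There is a second worry about counting. Read literally, a child with one dose and only a Day 1 sample might meet all three ANPS conditions while entering no post-vaccination estimate. Two programmers could then print different ANPS totals from the same text. The proposed remedy was to restrict ANPS at Months 7, 18 and 30 to children who received every scheduled dose, to say how Day 1-only children are counted, and to report non-completers beside the results, with an optional bound that counts them as failures.

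**Working it through.** **The plan's own figures (9.9).** With 95 evaluable children and a true rate of 99%, exact Clopper-Pearson limits give:
- Half-width at 94/95: (99.97 − 94.27)/2 = 2.85 points, against the stated figure of about 3.
- The lower limit reaches 90% when at least 92 of 95 convert (92/95 gives 91.05%; 91/95 gives 89.57%). P(X ≥ 92) = 0.9845 for one type. For all nine types, assuming independence, 0.9845^9 = 0.869, close to the stated 0.88.
- P(point estimate > 90%) needs at least 86 of 95 and exceeds 0.99 for all nine types.

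All of these are built on evaluable children, so the ANPS entry rule does not touch them.

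**Who can contribute after vaccination.** Compare the doses allowed by the ANPS rule with the doses that permit serum under 8.9.3 and 8.1.10.

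| Arm | ANPS as written | Serum permitted | Contributing, as written | Contributing, if all doses were required |
|---|---|---|---|---|
| 2-dose | 1 or 2 | 2 | 2 | 2 |
| 3-dose | 1, 2 or 3 | 3 | 3 | 3 |

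The last two columns agree in each arm. If the sampling rules are followed, the two wordings give the same numerators, denominators, intervals and GMTs.

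**Illustration.** Inputs: 100 children per arm (9.9), all assumed vaccinated and seronegative at Day 1, all completers assumed to have evaluable serum and to convert, and k non-completers. The documents do not give k. The 5% allowance in 9.9 covers discontinuation and PPI exclusions together, so k = 0 to 5 is an assumed range. When all convert, the exact lower limit is 0.025^(1/n) with n = 100 − k.

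| k | ANPS, either wording | Lower limit | Non-completers counted as failures | Lower limit |
|---|---|---|---|---|
| 0 | 100/100 | 96.38% | 100/100 | 96.38% |
| 1 | 99/99 | 96.34% | 99/100 | 94.55% |
| 2 | 98/98 | 96.31% | 98/100 | 92.96% |
| 3 | 97/97 | 96.27% | 97/100 | 91.48% |
| 4 | 96/96 | 96.23% | 96/100 | 90.07% |
| 5 | 95/95 | 96.19% | 95/100 | 88.72% |

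The right-hand columns answer a different question, namely seroconversion among everyone who started vaccination, with every non-completer assumed to fail. The objectives in Section 3 ask about children who received 3 or 2 doses. Under 9.3 the study is estimation only, so no threshold is crossed or missed.

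**The Day 1-only child.** Seronegativity at Day 1 already requires an evaluable Day 1 result. If that sample alone met the serum condition, the condition would add nothing. The natural reading is that it means post-vaccination serum, so such a child is outside ANPS. Whichever total is printed in a table header, 9.6.1 fixes the seroconversion denominator.

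**What ANPS does add to PPI.** It brings in completers with a dose outside the Table 5 ranges, Month 7 serum outside 21 to 49 days, an incorrect dose, or another protocol violation.

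**The case for a change.** The best case for a change is that ANPS is the only supportive population in Table 7, so readers will lean on it as the robustness check. The Schedules of Activities mark serum at Months 7, 18 and 30 without the exception in 8.9.3, so someone reading only those tables and 9.5.1 would not see the restriction. Table 7's dose labels cover Month 7 only. A sentence of clarification would cost almost nothing and could go in the supplemental SAP.

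Part of this stands. Agreement between PPI and ANPS is no evidence about non-completion, and whoever writes the report should not present it as such. But the plan makes no such claim. It calls ANPS supportive and nothing more. For Months 18 and 30, 8.9.3 covers later visits explicitly and 9.6.1 again counts only evaluable results for seropositivity. The counts a reader needs to judge non-completion are largely planned already in 9.11 and 9.6.3.

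The completers-only sentence is also not neutral. The equivalence shown above holds only if the sampling rules are followed. Section 9.5.2 foresees a boy allocated to 3 doses who receives 2, and Month 7 serum could be drawn from him in error. The present wording would keep that sample in ANPS, whereas the restriction would remove it and narrow the supportive population.

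**Conclusion.** No change is needed. The mismatch between the one-dose entry rule and the sampling rules is real, but it is a matter of wording that analysts will resolve from 8.9.3, 8.1.10, 9.6.1 and Table 7. Its effect on the planned estimates is zero, provided that no serum is taken from children who missed a dose. Stray samples of that kind would be the only place where the two definitions differ, and their number cannot be known from the documents. The primary and secondary objectives are answered as written. The gap of up to 7.5 points between lower limits at k = 5 (96.19 − 88.72 = 7.47) measures an extreme assumption about a question the study does not pose, and is not a defect in the plan.
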